## 1. Background

Overactive bladder syndrome (OAB) is defined by the International Continence Society (ICS) as “urinary urgency, usually accompanied by frequency and nocturia, with or without urinary urge incontinence, in the absence of urinary tract infection (UTI) or other obvious pathology (Haylen et al., 2010a, b). OAB affects at least 15% of adult women, with higher incidence with aging (Hartmann et al., 2009). By 2018, the prevalence of OAB worldwide is estimated to rise to over 20% (Irwin et al., 2011). Rates of OAB in urogynecologic patients with pelvic organ prolapse (POP) or urinary incontinence (UI) are as high as 88% (de Boer et al., 2010; Sajadi and Vasavada, 2010).

OAB symptoms can be caused by multiple etiologies, including bladder infection, malignancy, or neurological disease, e.g. multiple sclerosis or spinal cord injury (Mostwin, 2002). For most patients with OAB, however, the exact cause is unknown. One current theory is that OAB results from dysregulation in the neural pathways controlling micturition. Thus, the current medications for OAB are anticholinergic medications that target the muscarinic receptors in the detrusor muscle of the bladder (Michel and Chapple, 2009).

Mirabegron is an exciting new oral medication marketed by Astellas for OAB. It is a  $\beta$ 3-adrenergic receptor agonist that relaxes the detrusor smooth muscle during the urine storage phase, increasing bladder capacity. At usual clinical doses, mirabegron is believed to display selectivity for the  $\beta$ 3-adrenergic receptor subtype compared to its affinity for the  $\beta$ 1- and  $\beta$ 2-adrenoceptor subtypes. Data support that  $\beta$ -adrenoceptors, predominately the  $\beta$ 3 subtype, mediate detrusor smooth muscle tone and promote the storage function of the human bladder. Efficacy is seen within 8 weeks; steady state achieved within 7 days. Mirabegron can be effective for some patients, providing good symptom relief. Most studies, however, have documented that many patients (~50%) do not experience these preferred results (Chapple et al., 2014a; Chapple et al., 2014b).

Any attempt to understand mirabegron's influence on clinical symptoms should take into account our recent discovery of the female urinary microbiome (FUM) ([name] et al., 2014; Hilt et al., 2014; Pearce et al., 2014; [name] et al., 2012). The following observations support our hypothesis that the FUM exists and that it contributes to OAB and patient response to treatment. First, the bladders of women with and without lower urinary tract symptoms contain a FUM ([name] et al., 2014; Fouts et al., 2012; Hilt et al., 2014; Khasriya et al., 2013; Pearce et al., 2014; Siddiqui et al., 2011; [name] et al., 2012). Second, the bacteria that comprise the FUM are clearly distinct from those that cause overt clinical urinary tract infection (UTI) (Hilt et al., 2014; Pearce et al., 2014; [name] et al., 2012). Third, the FUM is associated with pre-treatment OAB symptoms and protection against UTI ([name] et al., 2014). Fourth, several bacterial species are more common in OAB patients than in asymptomatic controls (Pearce et al., 2014). Finally, response to an Astellas OAB anti-cholinergic treatment (solifenacin) varies according to FUM status (see *Preliminary Data*). These exciting findings open previously unappreciated opportunities for scientific inquiry concerning prevention, etiology and treatment of OAB.

These exciting findings with solifenacin should be replicated in clinically relevant populations treated with mirabegron, as it would be advantageous to identify affected individuals who are likely to respond prior to prescription. Currently, physicians have limited ability to meaningfully personalize UUI pharmacologic treatment and thus broadly prescribe too many affected individuals, including those who are likely to have minimal symptom relief. Since the FUM can be assessed prior to treatment, we propose to determine if baseline FUM assessment can provide insight into future symptom relief

with mirabegron treatment.

We propose the following hypothesis:

***In UUI-affected women treated with mirabegron, changes in urinary urgency incontinence are associated with changes to the FUM.***

## **2. Objectives:**

- A. In UUI-affected women treated with mirabegron, correlate patterns of urinary urgency relief with FUM characteristics.
- B. To develop clinically useful predictors for treatment response.

## **3. Materials and Methods:**

Following IRB approval, we will enroll 120 women with OAB. Human-research certified researchers will approach potentially eligible Loyola patients seeking care at the women's health or urogynecology clinics.

### ***Inclusion criteria:***

- Botherome idiopathic (non-neurologic) UUI who recall  $\geq 5$  urgency predominant urinary incontinence episodes in the prior week (urgency urinary incontinence or mixed urinary incontinence-urgency predominant) (Kenton et al., 2006); and
- No contraindications to taking mirabegron.
- Drug-naïve patients will account for at least 50% of enrolled participants. Patients on current OAB therapy will undergo a two-week drug washout period prior to baseline assessment in this study.

### ***Exclusion criteria:***

- Neurologic disease known to affect the lower urinary tract,
- Systemic immunologic deficiency,
- Current UTI (based on dipstick assessment) or recurrent culture-proven UTIs,
- History or current pelvic malignancy or radiation,
- Untreated symptomatic POP > POP-Q Stage II, or
- A contraindication to receiving mirabegron.

We also will exclude women of childbearing potential who are pregnant or nursing, or intend to become pregnant during the study, or who are not practicing a reliable method of contraception. Finally, patients must have not taken any antibiotics, for any reason, in the 4 weeks prior to enrollment (Smith et al., 1997).

### **Rescreening Opportunities:**

- Patients who had POP/UI surgery during the prior 12 weeks are ineligible, but may be rescreened at a later time.
- Patients on current OAB therapy can participate after undergoing a two-week drug washout period.

**Procedures:** Eligible woman will undergo an informed research consent process, which will be documented in their medication record. Participants who provide consent and sign the IRB-approved research consent form will complete a series of questionnaires that will be used to quantify symptoms. Symptom quantification will permit patient stratification based on phenotype. Stratification will be used to assess symptom-based correlates of response status. To quantify symptoms, we will use the following validated questionnaires: Urgency Severity and Life Impact Questionnaire (USIQ) (Lowenstein et al., 2012), Overactive Bladder Questionnaire (OAB-q) (Coyne et al., 2002), Urinary Distress Inventory (UDI-6) Pelvic Floor Distress Inventory (PFDI) (Barber et al., 2011), and Patient Global Impression of Severity (PGI-S) (Tincello et al., 2013).

From each patient-participant, a urine sample will be obtained by transurethral catheter and cultured (by standard clinical microbiology protocol) as part of their normal clinical evaluation. A portion of this urine will be saved for purposes of this study, but will be discarded if the patient declines study participation.

Once the research team confirms that the clinical culture is negative and the patient accepts the clinical recommendation for OAB oral medication, the patient-participant will be supplied with 25 mg daily of free mirabegron. Per the study protocol, the patient will be provided the free medication for the 12-week duration of the study.

Consistent with clinical follow-up for OAB treatment, the OAB patient-participants on mirabegron will return at 4, 8 and 12 weeks. In addition to their care, at each visit, each patient-participant will have her symptoms assessed by the questionnaires listed above and undergo catheterization for collection of urine specimen. To determine medication response, we will use the validated Patient Perception of Bladder Control (PPBC) (Coyne et al., 2006). If a subject's symptoms are adequately controlled with mirabegron 25 mg daily (based on a PPBC score of 4 or 5), she will continue at that study medication dose for the entirety of the study (an additional 8 weeks for a total of 12 weeks) and she will be considered a member of the 25-mg responder cohort. If a subject does not feel that they have adequate symptom control at 4 weeks (based on a PPBC score of 1, 2 or 3), she will be offered a dosage increase to 50 mg. At 12 weeks, if she feels that her symptoms are adequately controlled (based on a PPBC score of 4 or 5), then she will be considered to be a member of the 50-mg responder cohort. If, at 12 weeks, she feels that she does not have adequate symptom control, she will be considered a member of the non-responder cohort. The primary outcome, medication response, will be obtained at the end of the study (i.e., 12 weeks).

Consistent with clinical care, any patient with an active UTI will undergo catheterization for collection of a urine specimen with subsequent appropriate antibiotics, as indicated and consistent with the patient's allergy profile. For patient-participants who have a UTI at the time of a study visit, we will defer the completion of questionnaires and repeat catheterized urine specimen to the subsequent week in order to ensure appropriate clinical care of the UTI.

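### The 25-mg responder label is fixed by the week-4 PPBC with no week-12 condition, although the primary outcome is stated to be the response at 12 weeks

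*Protocol*

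**What the plan says.** The rule is in the follow-up paragraph of the Procedures in Protocol Section 3 (Materials and Methods). Women "will return at 4, 8 and 12 weeks". The response instrument is named: "To determine medication response, we will use the validated Patient Perception of Bladder Control (PPBC").

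- **25-mg responder.** The condition is "If a subject's symptoms are adequately controlled with mirabegron 25 mg daily (based on a PPBC score of 4 or 5"). She then stays on that dose for the rest of the study, described as "an additional 8 weeks for a total of 12 weeks", "and she will be considered a member of the 25-mg responder cohort".
- **50-mg responder.** A woman with PPBC 1, 2 or 3 at week 4 is offered an increase to 50 mg. If she scores 4 or 5 at week 12, "then she will be considered to be a member of the 50-mg responder cohort".
- **Non-responder.** The next sentence assigns this label to a woman who lacks adequate control at week 12.
- **Timing of the primary outcome.** The paragraph closes: "The primary outcome, medication response, will be obtained at the end of the study (i.e., 12 weeks").

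No other section defines the cohorts or says how to classify a woman who loses control after week 4 or who declines the increase. Section 8 says that no statistical analysis plan exists, so the protocol sends the reader nowhere else for the answer.

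**The concern.** The sentence on the 25-mg cohort does not itself name a visit. Its remaining period of 8 weeks out of 12 places the decision at week 4, and the following sentence gives the contrasting case explicitly at 4 weeks. One of the three cohorts is thus closed at week 4, while the other two are open until week 12. An early responder needs one good score at week 4; every other woman needs a good score at week 12.

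This matters because response is the variable on which both objectives in Section 2 rest: relating symptom relief to FUM characteristics and building predictors of treatment response. The hypothesis in Section 1 concerns changes in incontinence alongside changes in the FUM, and urine is collected at each visit. If the response label belongs to week 4 in some women and to week 12 in others, two analysts could derive different primary outcomes from the same data, and the label would not be aligned in time with the specimens.

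A second, smaller gap concerns the dose named in the label. The increase is only offered, and the 50-mg responder label does not require that 50 mg was accepted or taken.

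**Working it through.** The protocol gives no response, relapse or refusal rate, so there is no stated figure to reproduce. The check has a textual part and an illustration of size.

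**Step 1: the two rules side by side.**

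| Week-4 PPBC | Week-12 PPBC | Cohort rule | Read at week 12 |
|---|---|---|---|
| 4-5 | 4-5 | 25-mg responder | controlled |
| 4-5 | 1-3 | 25-mg responder | not controlled |
| 1-3 | 4-5 | 50-mg responder | controlled |
| 1-3 | 1-3 | non-responder | not controlled |

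The rules disagree only in the second row, and always in the same direction: responder by cohort, uncontrolled at week 12. The cohort rule can therefore never give fewer responders than a week-12 rule.

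**Step 2: how many women.** From the protocol: N = 120 ("we will enroll 120 women with OAB"). Assumed: a share s = 30-50% controlled at week 4, and a share r = 10-30% of those uncontrolled at week 12. Affected women = N × s × r.

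- Low end: 120 × 0.30 × 0.10 = 3.6, or 3% of 120.
- High end: 120 × 0.50 × 0.30 = 18.0, or 15% of 120.

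**Step 3: direction of bias in the FUM association.** Assume a marker present in 60 women and absent in 60, with 35 and 19 true week-12 responders (54/120 = 45%).

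- True odds ratio: (35 × 41)/(25 × 19) = 1435/475 = 3.02.
- Now label 18 relapsers as responders. The apparent response rate becomes 72/120 = 60%. The odds ratio depends on how those 18 divide between marker-positive and marker-negative women:
  - in proportion to true non-responders (25:41, i.e. 6.8 and 11.2): (41.8/18.2)/(30.2/29.8) = 2.27;
  - equally (9 and 9): (44/16)/(28/32) = 3.14;
  - in proportion to true responders (35:19, i.e. 11.7 and 6.3): (46.7/13.3)/(25.3/34.7) = 4.8.
- With 4 relapsers split equally: (37/23)/(21/39) = 2.99, and the apparent rate is 58/120 = 48.3%.

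The odds ratio can fall, stay nearly the same or rise.

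**Step 4: declined escalation.** Women offered 50 mg: 120 × (1 − 0.50) = 60 to 120 × (1 − 0.30) = 84. Assume that 10-20% decline and that 20-40% of those who decline are controlled at week 12.

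- Low end: 60 × 0.10 × 0.20 = 1.2.
- High end: 84 × 0.20 × 0.40 = 6.7.

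About 1 to 7 women would fit the 50-mg responder wording without having taken 50 mg.

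**The case against.** The strongest defence is that the week-4 step only names a dose path, and that the closing sentence on the primary outcome, together with the non-responder sentence, settles response at week 12 for everyone. The closing sentence does support a week-12 outcome for all. The non-responder sentence is weaker support, because its subject follows on from the woman offered the increase. If it is stretched to cover all women, a relapser on 25 mg belongs to the 25-mg responder cohort and the non-responder cohort at once. The conflict remains on either reading. What stands is that a reader should not infer that the protocol has decided to score relapsers as responders on the primary outcome. It says two incompatible things, and relapse is not addressed.

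Other stronger readings are tempting but not supported:

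- **That the FUM association is diluted.** This needs relapsers to resemble other non-responders in their FUM. They are by definition week-4 responders and may carry more of a response marker. Step 3 shows movement in either direction.
- **That every woman who declines 50 mg lacks a correct cohort.** One who is uncontrolled at week 12 fits the non-responder wording. One who is controlled is a responder under any dose label, so only the label is wrong.
- **That the week-12 PPBC is already listed for all women.** The primary-outcome sentence implies it, but the questionnaire list repeated at each visit omits the PPBC, and Section 5 lists it without visits.

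It is also fair to say that every rate used above is assumed and that 18 women is an extreme. It takes 50% controlled by week 4, which equals the overall response implied by the roughly 50% without good relief cited in Section 1, where efficacy is said to appear within 8 weeks. Finally, the study has a single treated group, so no comparison between treatments is biased.

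**Conclusion.** The point holds as a contradiction within the protocol's own definition of its primary outcome. It does not depend on any assumed rate, and it is not a detail that an analysis plan would normally supply, because the protocol fixes the cohorts itself and fixes them inconsistently.

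Its size is uncertain. About 4 to 18 of 120 women (3-15%) would be classified differently under the two rules, given the assumed 30-50% control at week 4 and 10-30% later loss of control. The effect on the apparent response rate is upward or nil. The effect on the FUM association has no predictable sign. The declined-escalation gap is secondary: about 1 to 7 women under the stated assumptions, with no effect on response versus non-response.

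**What to change.** Reconcile the sentences in the follow-up paragraph of Section 3 so that outcome classification uses one time point:

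- Define primary response for every woman by the week-12 PPBC, using the cut-off the protocol already applies: 4 or 5 is a responder and 1 to 3 a non-responder, whatever the week-4 score.
- State that the PPBC is obtained at week 12 in all women, including those controlled at week 4.
- Name the responder sub-cohorts by the dose actually taken, which also settles the label for a woman who declined the increase.
- Keep week-4 response as a separate secondary outcome.

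This concerns classification only; no dosing rule changes. The cost is a wording change and, if the week-12 PPBC was not already planned for everyone, one short questionnaire at an existing visit. The reported response rate may be slightly lower.

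### The dose-named responder cohorts cannot separate response to 50 mg from longer time on treatment, and the 50-mg label does not depend on the dose taken

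*Protocol*

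**What the plan says.** Section 1 (Background) says of mirabegron: "Efficacy is seen within 8 weeks; steady state achieved within 7 days". It ties neither figure to a dose.

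In section 3 (Procedures), once the clinical culture is negative, "the patient-participant will be supplied with 25 mg daily of free mirabegron", and "the OAB patient-participants on mirabegron will return at 4, 8 and 12 weeks". The cohorts are then built as follows:

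- A woman with PPBC 4 or 5 at week 4 stays on 25 mg for "an additional 8 weeks for a total of 12 weeks) and she will be considered a member of the 25-mg responder cohort".
- The other branch begins "If a subject does not feel that they have adequate symptom control at 4 weeks (based on a PPBC score of 1, 2 or 3"; in that case "she will be offered a dosage increase to 50 mg".
- If such a woman has PPBC 4 or 5 at week 12, "then she will be considered to be a member of the 50-mg responder cohort". Otherwise she is a non-responder.

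The same paragraph closes with the endpoint: "The primary outcome, medication response, will be obtained at the end of the study (i.e., 12 weeks".

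**The concern.** The two responder cohorts carry dose names, but they differ in three ways at once: the dose offered, the time on treatment when the label is earned, and the fact that one group has already been uncontrolled at week 4. A cohort named for a dose invites the reading that its members needed that dose.

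Section 2 aims to relate symptom relief to the urinary microbiome and to derive usable predictors of response. If baseline or on-treatment microbiome features differed between the two responder cohorts, the labels would point to dose, although the difference might lie only between early and late control. There is also a plain classification gap: the increase is an offer, yet the week-12 sentence assigns the label by PPBC alone.

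**Working it through.** The protocol gives no figure for this split, so there is none to reproduce. The check sets the rules side by side and then asks what the data could identify.

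**Inputs from the protocol:** 120 women to be enrolled, one treated group, all starting on 25 mg (section 3); visits at weeks 4, 8 and 12 (section 3); efficacy within 8 weeks (section 1).

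**Inputs not in the protocol (assumptions below):** the share controlled at week 4; the chance *t* that a woman uncontrolled at week 4 would be controlled by week 12 on unchanged 25 mg; the chance *d* that the higher dose brings control among the rest.

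**Step 1. Timelines.**

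| Label | Earned by | Weeks on drug when earned | Dose history |
|---|---|---|---|
| 25-mg responder | PPBC 4–5 at week 4 | 4 | 25 mg |
| 50-mg responder | PPBC 1–3 at week 4, 4–5 at week 12 | 12 | 25 mg for 4 weeks, then up to 12 − 4 = 8 weeks on 50 mg if accepted; not stated if declined |

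Against the 8-week bound, 8 − 4 = 4 weeks of the stated onset window remain when the cohorts divide.

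**Step 2. Routes to the 50-mg label.** Three fit the wording: late control that 25 mg would have produced anyway; control brought by the higher dose; control in a woman who declined the increase. The week-8 visit does not separate the first two, because it falls after the increase.

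**Step 3. What can be identified.** Suppose every offer is accepted and the increase never lowers response. Among women uncontrolled at week 4, the observable proportion controlled at week 12 is p = t + (1 − t)d, and the late-response share of the 50-mg cohort is t/p. That is one observed quantity for two unknowns. For illustration, assume 30% are controlled at week 4, so 120 × 0.70 = 84 are not, and p = 0.28, giving a cohort of 84 × 0.28 = 23.5 women. All four rows below produce that same cohort:

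| t | d | p | Late-response share t/p |
|---|---|---|---|
| 0 | 0.28 | 0.28 | 0% |
| 0.10 | 0.20 | 0.10 + 0.90 × 0.20 = 0.28 | 36% |
| 0.20 | 0.10 | 0.20 + 0.80 × 0.10 = 0.28 | 71% |
| 0.28 | 0 | 0.28 | 100% |

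The table estimates nothing. It shows that identical data fit any share from none to all, because every accepted increase coincides with further weeks on treatment and nobody is kept on 25 mg by design for comparison.

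**Step 4. Week 4 against week 12.** The 25-mg label is assigned at week 4 and the text gives no later check on it. A woman controlled at week 4 but not at week 12 keeps a responder label, although the primary outcome is taken at week 12.

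**The case against.** The strongest reply is that no harm is documented. The hypothesis, the objectives and the primary outcome all speak of symptom change or medication response, and none is specific to a dose. Nowhere does the protocol plan a microbiome contrast between the two responder cohorts. This stands: a reader might infer from the labels that a dose-related phenotype will be claimed, but the documents do not say so.

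Second, the onset statement is an upper bound without a dose or a PPBC threshold. It is compatible with nearly all response appearing by week 4. This also stands. A reader might infer that late 25-mg responders are in fact credited to 50 mg, or that they make up much of the cohort. The text shows only that this is possible. Nor do sections 1 and 3 contradict each other outright.

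Third, the sentence on the 50-mg cohort follows directly on the dose increase and most naturally describes women who took it. That is fair, but on that reading a woman who declines and is controlled at week 12 has no cohort at all. The rule needs a clause either way.

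Fourth, the choice of primary contrast is often left to an analysis plan, and a pooled week-12 comparison can already be formed from the planned data. True, but the cohorts are defined in the protocol itself, and section 8 says that there is no analysis plan. The point concerns a stated rule, not a missing detail. None of these replies restores the ability to separate dose from time.

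**Conclusion.** The structural point holds. As written, the 50-mg responder label cannot tell response to the higher dose from later response to 25 mg, and it does not depend on the dose taken. This rests on the protocol's text alone and needs no assumed rates.

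The size of any misattribution is unknown and may be zero. A pooled responder versus non-responder comparison is free of the dose-label problem, provided that all women are classified at week 12. The weakness is thus confined to the dose-named split and to the week-4 fixing of the 25-mg cohort. It is worth correcting because the correction is cheap and the design offers no way to repair the labels afterwards.

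**What to change.** - Define the primary outcome for every woman as responder or non-responder by PPBC at week 12, pooled over dose, including those already controlled at week 4.
- Report the split only descriptively, as controlled at week 4 and controlled at week 12 but not at week 4, tabulated by the dose actually taken. Record that dose, so that a woman who declines the increase is classified correctly.
- State that no dose-specific microbiome conclusion will be drawn from the split.
- Reconcile the week-4 cohort assignment in section 3 with the week-12 primary outcome in the same paragraph and with the 8-week statement in section 1.

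No change of dose, titration time or dosing rule is proposed. The cost is rewording and a record of the dose taken. Dose-specific microbiome readings are given up, but the design cannot support them.

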#### **5. Data Collection:**

We will collect demographic data (age, race, BMI, medical co-morbidities, tobacco use, medical history including estrogen status, and surgical history) on all participants. We will also collect the responses of the USIQ, PFDI, OABq and UDI-6, PGI-S, and PPBC. The urine specimens will be split into two specimens, one will be sent to the clinical microbiology laboratory for routine culture while the other de-identified specimen will be sent to the [name] laboratory for EQUIC and sequencing.

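### The 25-mg responder label is tied to week 4 and the non-responder label to week 12, so women who leave early after poor control belong to no cohort

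*Protocol*

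**What the plan says.** The cohort rules are in Protocol section 3, in the Procedures text printed under Rescreening Opportunities.

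- **Controlled on 25 mg (PPBC 4 or 5).** The woman stays on that dose: "she will continue at that study medication dose for the entirety of the study (an additional 8 weeks for a total of 12 weeks". The same sentence adds that "she will be considered a member of the 25-mg responder cohort".
- **Not controlled at week 4 (PPBC 1, 2 or 3).** No label is given at this visit; "she will be offered a dosage increase to 50 mg". She becomes a 50-mg responder if her PPBC is 4 or 5 at week 12.
- **Non-responder.** "If, at 12 weeks, she feels that she does not have adequate symptom control, she will be considered a member of the non-responder cohort".
- **Timing of the outcome.** "The primary outcome, medication response, will be obtained at the end of the study (i.e., 12 weeks".

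Section 5 lists what is collected: demographics and history, the urine specimens, and the questionnaires ("We will also collect the responses of the USIQ, PFDI, OABq and UDI-6, PGI-S, and PPBC"). It names neither a date nor a reason for stopping mirabegron. Section 8 states that no statistical analysis plan exists, so the protocol does not pass the question to another document. No dropout rate, denominator or rule for women without a week-12 assessment is given.

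**The concern.** The three labels are not assigned on the same footing. Early success can be recorded at week 4. Failure can be recorded only in a woman who is still being assessed at week 12. A woman who is uncontrolled and leaves is therefore removed from the classification, while a woman who is controlled and then leaves appears to stay in it.

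This bears on Objective B, the development of predictors of treatment response. A predictor of response needs non-responders to compare with responders. If the women with the poorest relief or tolerance are the ones most likely to leave, those who remain as non-responders are a selected group. Any link between the baseline microbiome and response is then estimated against that selected group. A response rate quoted among classified women would also be too high.

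**Working it through.** **The rules applied to women who leave**

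| Course | Label under the cohort sentences | Label if the week-12 sentence governs |
|---|---|---|
| Leaves in week 2 | none | none |
| PPBC 1 to 3 at week 4, leaves in week 6 | none | none |
| PPBC 4 or 5 at week 4, leaves in week 6 | apparently 25-mg responder | none |
| PPBC 1 to 3 at week 4, assessed at week 12 and uncontrolled | non-responder | non-responder |

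Week 4 for the 25-mg label is inferred: visits are at 4, 8 and 12 weeks, and 12 − 8 = 4. The second and third rows show the asymmetry. On the other reading the asymmetry goes, but all early leavers are unclassified.

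**Inputs**

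- N = 120, from section 3 ("we will enroll 120 women with OAB"). The protocol gives no calculation behind this figure, so there is nothing to reproduce.
- True response of 50%, borrowed for illustration from section 1 ("many patients (~50%) do not experience these preferred results"): 60 responders and 60 non-responders.
- Dropout is not stated. All values below are assumptions.

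**Scenario 1: only non-responders leave.** Rate among classified women = R / (N − L), with R responders and L leavers.

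- 10% of non-responders leave (L = 6): 60/114 = 52.6%; 54 non-responders remain.
- 20% leave (L = 12): 60/108 = 55.6%; 48 remain.
- 30% leave (L = 18): 60/102 = 58.8%; 42 remain.
- With all 120 as denominator: 60/120 = 50.0% in every case.

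With the same 6, 12 and 18 leavers, a true rate of 40% becomes 48/114 = 42.1%, 48/108 = 44.4% and 48/102 = 47.1%. A true rate of 60% becomes 72/114 = 63.2%, 72/108 = 66.7% and 72/102 = 70.6%.

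**Scenario 2: dropout after week 4 unrelated to outcome, week-4 label kept.** Let x be the share controlled at week 4, q the week-12 response among the rest, and d the dropout. With a true rate of 50%, q = (0.5 − x)/(1 − x), and

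rate = [x + (1 − x)q(1 − d)] / [x + (1 − x)(1 − d)].

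- x = 0.2, q = 0.375: d = 0.1 gives 0.47/0.92 = 51.1%; d = 0.2 gives 0.44/0.84 = 52.4%.
- x = 0.4, q = 0.167: d = 0.1 gives 0.49/0.94 = 52.1%; d = 0.2 gives 0.48/0.88 = 54.5%.

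The timing difference alone thus adds about 1 to 4.5 points.

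**Scenario 3: no dropout, but control is lost after week 4.** If 10% to 30% of week-4 responders (20% to 40% of women) are uncontrolled by week 12 and keep the label, the rate is overstated by 0.2 × 0.1 = 2 points to 0.4 × 0.3 = 12 points.

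**The case against.** The best reply is that the protocol sets the primary outcome at 12 weeks, and that the 25-mg sentence joins cohort membership to completing 12 weeks. No text says that a woman who leaves keeps the label. That is a fair reading, which is why this point says only that she appears to keep it. It does not give the other leavers a cohort, and it leaves two timing statements that do not agree.

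Several stronger conclusions are tempting, and the documents do not support them.

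- **That the response rate is inflated.** This needs dropout, and a denominator restricted to classified women. The protocol states neither. With all 120 as denominator, unlabelled leavers do not raise the rate. Nor is estimating a response rate a stated objective.
- **That stopping the drug means no week-12 PPBC.** No rule withdraws women who stop. One who attends week 12 uncontrolled fits the non-responder rule. Equally, no rule requires that she be followed.
- **That the non-responder cohort holds only women who accept catheterization.** A specimen is planned at each visit, but nothing makes the PPBC conditional on it.
- **That leavers could never be placed afterwards.** Some will have a week-4 or week-8 PPBC or an adverse-event report. The gap is that no rule uses them, and section 5 lists no stop date or reason.
- **That every microbiome comparison is affected.** The hypothesis and Objective A can be addressed through symptom change without the cohorts.

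Counting every woman who stops for an adverse event as a treatment failure is also debatable: response is defined by PPBC, and that choice would mix intolerance with lack of control.

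**Conclusion.** The point holds in conditional form. The cohort definitions tie 25-mg response to week 4 without a re-check, allow non-response only at week 12, and conflict with the sentence that sets the outcome at 12 weeks. On either reading, a woman who leaves early after poor control has no outcome category. This is a defect in how the protocol defines its primary outcome, not a detail left to an analysis plan.

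If only classified women are analysed, the illustrative upward bias is about 3 to 9 points when 10% to 30% of non-responders and no responders leave, and about 1 to 4.5 points when 10% to 20% leave regardless of outcome. Both ranges assume a true response of 50%, and the second assumes that 20% to 40% are controlled at week 4. The more relevant harm is the depleted comparator, from 60 to as few as 42 in the first scenario. The size of any bias in the microbiome association cannot be computed from the protocol.

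**What to change.** 1. **Section 3, Procedures.** Reconcile the two timing statements so that every cohort label, including 25-mg responder, comes from the week-12 PPBC. This changes classification only, not dosing.
2. **Follow-up.** Seek the week-12 PPBC and questionnaires from every treated woman, including those who stop mirabegron. Use telephone or mail, without catheterization, if she will not attend.
3. **Section 5.** Add stop date and stop reason.
4. **Analysis set.** Keep every treated woman in the denominator. In the primary analysis, count a woman with no week-12 PPBC as not having shown response. Run sensitivity analyses that count such women each way, and that separate stopping for adverse events from stopping for lack of effect.

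The sensitivity analyses matter because the primary rule can understate response. With 60 true responders among 120 and 12 leavers split 6 and 6, it gives 54/120 = 45%; counting all leavers as responders gives 66/120 = 55%. Obtaining the PPBC from leavers narrows that gap.

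The cost is a short amendment, a few form fields, one contact per leaver, and a reported response rate that may be lower.
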